1. SYNOPSIS

Protocol Title:	A Pilot, Open-Label Study to Evaluate the Safety, Tolerability, and Performance of the FAST PV Technology in Chronic Dialysis Patients with Extremely reduced or no Kidney Function																						
Indication:	Quantitative determination of plasma volume (PV) and interstitial volume (ISV)																						
Investigators and Clinical Research Units:	Patients will be recruited and evaluated at a single site located in the United States.																						
Objectives:	
Primary:
 
 To evaluate PV and ISV using the FAST PV Technology and iohexol in patients on chronic dialysis predialysis. To evaluate the interaction between PV and ISV measured after a dialysis with a repeat injection of VFI using the FAST PV Technology. To assess the safety and tolerability of visible fluorescent injectate (VFI)TM (employing the FAST PV Technology) in chronic dialysis patients with extremely reduced or no renal function. 																						
Endpoints:	
Primary:
 
 To measure quantitatively the ISV and PV of patients pre and post dialysis using the FAST PV Technology and Iohexol measurement. Directly compare quantitative difference of ISV and PV measured by the FAST PV Technology and Iohexol measurement to the volume removed during dialysis. To assess safety through adverse events (AEs) and serious adverse events (SAEs), clinical laboratory tests, physical examination findings and vital signs. 																						
Study Design:	
This is a pilot, single-center, open-label study designed to evaluate the safety, tolerability, and performance of the FAST PV Technology in patients on chronic dialysis.
 
The planned dose cohorts are presented in the table below:
 
  
 Cohort	Population	eGFR^a	Base VFI Dose^b	Number of Doses	Comparator Dose	Number of Doses	Number of Subjects	
   
 1	Dialysis Patients	≤ 2 mL/min/1.73 m²	3 mL	2	Iohexol 5 mL	2	10	
  
 
Abbreviations: eGFR = estimated glomerular filtration rate; N/A = not applicable. ^a Patients must be on chronic hemodialysis for ≥ 3 months and oliguric defined as ≤ 2 urinary voids per day. ^b 3 mL for subjects/patients ≥ 40 and ≤ 100 kg + 1 mL for every 40 kg increase in body weight
 
Administration of VFI will occur within 28 days of screening.
 
Patients will receive 1 dose of VFI and 1 dose of iohexol approximately 4 hours prior to undergoing dialysis followed by a second dose of VFI and second dose of iohexol approximately 1 hour after completing dialysis. Patients will be discharged following completion of Day 1 activities. A follow-up visit will occur at the patient's next 2 dialysis appointments (approximately 2-3 days after Day 1) and 1 week after Day 1. A follow-up phone call will be performed on Day 31 (± 1 day).
							Cohort	Population	eGFR ^a	Base VFI Dose ^b	Number of Doses	Comparator Dose	Number of Doses	Number of Subjects	1	Dialysis Patients	≤ 2 mL/min/1.73 m ²	3 mL	2	Iohexol 5 mL	2	10
Cohort	Population	eGFR ^a	Base VFI Dose ^b	Number of Doses	Comparator Dose	Number of Doses	Number of Subjects																
1	Dialysis Patients	≤ 2 mL/min/1.73 m ²	3 mL	2	Iohexol 5 mL	2	10																
Subject Selection Criteria:	Males and females ≥ 18 will be enrolled in the study. Patients must be oliguric (have an estimated glomerular filtration rate (eGFR) ≤ 2 mL/min/1.73 m ²) and must be receiving maintenance chronic dialysis.																						
Investigational Product, Dose, and Route of	VFI, 3 mL for subjects/patients ≥ 40 and ≤ 100 kg + 1 mL for every 40 kg increase in body weight, bolus injection																						

Administration:	
Comparator, Dose, and Route of Administration:	Omnipaque™ 300 (iohexol), 647 mg of iohexol equivalent to 300 mg of organic iodine/1 mL (each mL of iohexol solution contains 1.21 mg tromethamine and 0.1 mg edetate calcium disodium), 5 mL, bolus injection
Criteria for Evaluation:	
Safety: Adverse events will be collected and evaluated as they occur throughout the study. Safety assessments, including physical examinations, vital signs, and clinical laboratory tests, will be performed at specified time points.
 
Performance: Measurements of PV and ISV will be determined using the FAST BioMedical Fluorescent Instrument (FBFI) and iohexol. Plasma Volume: Plasma volume will be determined using FAST PV Technology. Interstitial Volume: Interstitial Volume will be determined using the FAST PV Technology based on both FAST VFI and Iohexol plasma concentrations.

Planned Sample Size:	The anticipated sample size of approximately 10 is appropriate for pilot studies of similar design.
Statistical Analysis:	
Analysis Populations: Safety Population: All subjects who receive any amount of study product. Performance Population: All subjects who have either a PV or ISV measurement using any of the techniques under study.
 
Safety Analysis: The number and percentage of subjects reporting any treatment-emergent AE will be tabulated by system organ class, preferred term (coded using Medical Dictionary for Regulatory Activities), and cohort. Treatment-emergent AEs will be further classified by severity and relationship to study product. Vital signs and clinical laboratory test data (observed and change from baseline) will be summarized by cohort and time point using appropriate descriptive statistics. Physical examination findings results will only be listed.
 
Performance Analysis: PV and ISV Measurements determined by FAST PV Technology will be compared to measurements determined by iohexol for both Dose 1 and Dose 2. Basic statistical analyses including correlations and Bland-Altman plots will be performed. Changes in PV and ISV measurements between Dose 1 and Dose 2 determined by the FAST PV Technology and iohexol will be compared to the known volume of fluid removed during dialysis treatment. Basic statistical analyses including correlations and Bland-Altman plots will be performed. Residual amounts of FAST VFI will be assayed on the Day 3 and Day 8 follow-up visits to assess the continued removal of the FAST VFI in this patient population.

Table 1. Schedule of Assessments and Procedures						
Study Procedure	Screening^a	Day 1		Follow-Up		Discharge^b
	Days -28 to -2	Dose 1	Dose 2	Day 3	Day 8	Day 31
Informed consent	X					
Inclusion/exclusion criteria ^a	X	X				
Demographics	X					
Height	X					
Body weight	X	X	X			
BMI ^c	X	X				
Medical and surgical history	X	X ^d				
Physical examination	X	X				
Vital signs ^e	X	X ^f	X ^f			
Clinical laboratory tests ^g		X ^{gh}	X ^h			
Hematocrit		X ⁱ	X ⁱ			
nT pro-BNP		X				
Creatinine phosphokinase		X ^h		X	X	
Liver function tests		X		X	X	
Timed Urine Collection ^j		X	X			
Pregnancy test (nonmenopausal females only)	X	X				
Outpatient visit	X	X	X	X	X	X
FAST VFI administration		X	X ^k			
Iohexol administration		X	X			
FD001 and FD003 plasma samples		Refer to Table 2		X ^l	X ^l	
Iohexol plasma samples		Refer to Table 2				
Adverse events		X	X	X	X	X
Serious adverse events		X	X	X	X	X
Concomitant medications	X	X	X			

Abbreviations: BMI = body mass index; FD001 = 5 kD carboxymethyl dextran; FD003 = 150 kD carboxymethyl dextran; FSH = follicle-stimulating hormone; HBV = hepatitis B virus; HCV = hepatitis C virus; HIV = human immunodeficiency virus; VFI = visible fluorescent injectate.

^a. Assessments conducted upon enrollment will be used to reconfirm a subject's eligibility for enrollment into the study.

^b. Discharge procedures will be performed following completion of all Day 31 assessments. Subjects who terminate from the study early will have discharge procedures performed at the time of discontinuation.

^c. BMI will be calculated using the height obtained at screening.

^d. Medical and surgical history will be collected and documented to determine if any changes have occurred since screening.

^e. Vital signs will be measured after the subject has been resting quietly in a supine position or in the most recumbent position possible for at least 5 minutes.

^f. Vital signs will be measured within approximately 30 minutes prior to VFI and iohexol administrations and approximately 60-, 120- and 180-minutes post VFI and iohexol administrations.

^g. Refer to [Table 6](#) for a detailed list of clinical laboratory test parameters, which will be collected from the medical

Table 1. Schedule of Assessments and Procedures						
Study Procedure	Screening^a	Day 1		Follow-Up		Discharge^b
	Days -28 to -2	Dose 1	Dose 2	Day 3	Day 8	Day 31
record. h. BUN and serum creatinine will be drawn pre-dose dose 1 and post the dose 2 180 min VFI blood draw. i. Predose j. Pooled urine collection (from patient arrival to departure) to measure total volume, creatinine and urea nitrogen. No catheter. k. VFI administration of Dose 2 will occur approximately 8 hours following VFI administration of Dose 1 l. Blood samples to be drawn after dialysis session to allow for determination of any remaining FAST VFI. NOTE: In the event multiple postdose procedures are required to be conducted at the same nominal time point, the timing of performance blood sample collections will take priority over all other scheduled activities. In practice, the following order is recommended: (1) vital signs assessments; (2) performance blood sampling; (3) clinical laboratory tests sampling; (4) physical examination. Vital signs may be conducted up to 10 minutes prior to the nominal time to minimize the potential autonomic effects of blood draws on these measurements.						

Table 2. Performance Sampling Schedule – (Two Performance Periods)					
Nominal Time Relative to Start of VFI Bolus Injection	FD001 and FD003 Plasma Sample	Iohexol Plasma Sample	Volume of Blood drawn^b	Timed Urine Collection	
Predose (within 30 minutes)	X	X	6 mL	Pool urine from patient arrival to departure.	
0 minutes	VFI and Iohexol Administration				
15 minutes	X	X	7 mL		
60 minutes	X	X	7 mL		
80 minutes	X		4 mL		
120 minutes	X	X	7 mL		
180 minutes	X	X	7 mL		
Dialysis Treatment (4 hours)					
Pre- Rinseback	X		4 mL		
Equilibrium time Post-Dialysis (1 hour)					
Predose (within 5 minutes of drug administration)	X	X	7 mL		
0 minutes	VFI and Iohexol Administration ^a				
15 minutes	X	X	7 mL		
60 minutes	X	X	7 mL		
80 minutes	X		4 mL		
120 minutes	X	X	7mL		
180 minutes	X	X	7 mL		

Blood Samples will be drawn at approximately the times listed in Table 2.2; however due to the nature of the study some variation in timing may occur. Regardless of the time and number of blood draws, no subject will have more than 80 mLs blood drawn for this study within a 24-hour period.
 
Abbreviations: FD001 = 5 kD carboxymethyl dextran; FD003 = 150 kD carboxymethyl dextran; VFI = visible fluorescent injectate.
 
^{a.} Second VFI and iohexol administration will occur approximately 8 hours after the initial administrations.
 
^{b.} Each blood draw will be taken as follows: 1 mL waste draw, 3mL FAST blood sample, 3 mL Iohexol Sample Note: Blood samples will be collected from the venous side of the arteriovenous fistula/graft. Performance blood samples will be collected as close to the nominal time point as possible. The allowable window for postdose blood sample collection relative to the start of VFI/iohexol bolus injection will be ±5 minute.
					

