4.6.2. Rationale for Study Design

This is a pilot, single-center, open-label study designed to evaluate the safety, tolerability, and performance of the FAST PV Technology in chronic dialysis patients. The dosing schedule was determined based on anticipated clinical use.

Male and female subjects will be enrolled in the study. As no sufficient data are available on a potential influence of the VFI on embryo-fetal development, female subjects must be of non-childbearing potential or must provide confirmation of a known and medically acceptable contraception method. Reproductively active men must agree to either practice abstinence or utilize adequate contraception.

Subject safety will determine the progression or discontinuation of the study. In rare cases, dextran products have been documented to produce anaphylactic reactions in humans, and the onset of symptoms is documented to be acute. The VFI is a substituted dextran product that has shown little evidence of antigenicity in nonclinical studies.

The duration of confinement and medical surveillance are considered adequate to ensure safety of the subjects.

The FAST VFI has not been given to dialysis patients before. In the Phase 2c study, a patient with a measured GFR of 16.7 mL/min/1.73m² was dosed with VFI with no AE or SAEs related to the study drug observed. Although the patients in this study will receive 2 doses of FAST VFI, the initial doses of VFI and iohexol will be removed during the patient's dialysis session. The second dose of VFI and Iohexol will be removed between 36 and 48 hours later at the first follow-up dialysis session. The concentration the patients in this study will be exposed to is higher for longer than previous studies due to the lack of kidney function; however, the FD001 and iohexol, will continue to distribute into the extracellular fluid of the patient. The FD003 exposure is unchanged from prior studies.

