7.1. Inclusion Criteria

Subjects/patients must meet all inclusion criteria to be eligible for study participation.

1. Males or females ≥ 18 years of age.
2. Females must be of non-childbearing potential (eg, postmenopausal [defined cessation of regular menstrual periods for at least 1 year confirmed by age ≥ 60 or surgically sterile by hysterectomy, bilateral oophorectomy, or bilateral tubal ligation [documentation required]]) or be using a medically acceptable form of birth control (a barrier method, intrauterine device, or hormonal contraception) from screening through 30 days after administration of the last dose of VFI.
3. Males who are sexually active and whose partners are females of childbearing potential must agree to practice abstinence or use condoms from screening through 90 days after administration of the last dose of VFI, and their partners must be willing to use a medically acceptable method of contraception (a barrier method, intrauterine device, or hormonal contraception) from screening through 90 days after administration of the last dose of VFI.
4. Males must agree to not donate sperm from screening through 90 days after administration of the last dose of VFI.
5. Subjects/patients must be able to communicate effectively with the study personnel.
6. Patients must be on chronic hemodialysis for ≥ 3 months and oliguric defined as ≤ 2 urinary voids per day.
7. Patients must have an average interdialytic weight gain of at least 2 kg.
8. Patients must have an A-V dialysis shunt.
9. Patients must have a functioning A-V dialysis shunt, either fistula or graft.

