8.2. Treatments Administered

Each subject/patient will receive 2 doses of VFI and 2 doses of iohexol, which will be administered IV through a bolus injection. An IV catheter will be inserted into the subject's arteriovenous fistula or graft by an experienced dialysis nurse.

Patients will receive 1 dose of VFI and 1 dose of iohexol approximately 4 hours prior to undergoing dialysis followed by a second dose of VFI and second dose of iohexol approximately 1 hour after completing dialysis.

The dose of VFI will be 3 mL for subjects/patients ≥ 40 and ≤ 100 kg and will increase by 1 mL for every 40 kg increase in body weight as outlined in [Table 5](#).

Body weight		Dose (mL)	VFI (mg)	FD001 (mg)	FD003 (mg)	VFI (mg/kg)	FD001 (mg/kg)	FD003 (mg/kg)
(lbs)	(kg)							
88	40	3	47.01	35.01	12	1.18	0.88	0.300
154	70	3	47.01	35.01	12	0.67	0.50	0.171
220	100	3	47.01	35.01	12	0.47	0.35	0.120
223	101	4	62.68	46.68	16	0.62	0.46	0.158
309	140	4	62.68	46.68	16	0.45	0.33	0.114
311	141	5	78.35	58.35	20	0.56	0.41	0.142
397	180	5	78.35	58.35	20	0.44	0.32	0.111
399	181	6	94.02	70.02	24	0.52	0.39	0.133
485	220	6	94.02	70.02	24	0.43	0.32	0.109
487	221	7	109.69	81.69	28	0.50	0.37	0.127
573	260	7	109.69	81.69	28	0.42	0.31	0.108
575	261	8	125.36	93.36	32	0.48	0.36	0.123
661	300	8	125.36	93.36	32	0.42	0.31	0.107
664	301	9	141.03	105.03	36	0.47	0.35	0.120
750	340	9	141.03	105.03	36	0.41	0.31	0.106

A low-protein snack will be served prior to administration of VFI (eg, toast, bagel, Graham crackers, or primarily carbohydrate-based small portion). Water will be allowed as desired up to 1.5 liters, but must be tracked on the CRF. Meals appropriate for the patient’s medical condition will be served.

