11.3. Endpoints

11.3.1. Primary Endpoints

- To measure quantitatively the ISV and PV of patients pre and post dialysis using the FAST PV Technology and Iohexol measurement.
- Directly compare quantitative difference of ISV and PV measured by FAST PV Technology and Iohexol measurement to the volume removed during dialysis.
- To assess safety through adverse events (AEs) and serious adverse events (SAEs), clinical laboratory tests, physical examination findings and vital signs.

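### The primary change comparison sets the Dose 1 to Dose 2 change in PV and ISV against dialysis volume removed, but that change reflects net fluid balance, including what patients drink and eat in between

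*Protocol*

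**What the plan says.** The reference is set in the primary endpoint (Protocol, 11.3.1, and almost word for word in the Synopsis): "Directly compare quantitative difference of ISV and PV measured by FAST PV Technology and Iohexol measurement to the volume removed during dialysis". The Synopsis, under Performance Analysis, repeats it for the change between doses: changes by FAST and "iohexol will be compared to the known volume of fluid removed during dialysis treatment". It names correlations and Bland-Altman plots. Sections 11.5.1 and 11.5.2 say how PV and ISV are obtained and add no term for fluid taken in.

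The time between measurements is in Table 2, footnote a: "Second VFI and iohexol administration will occur approximately 8 hours after the initial administrations". Table 1, footnote k, agrees.

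Section 8.2 deals with intake: "Water will be allowed as desired up to 1.5 liters, but must be tracked on the CRF". It also provides a snack before VFI and meals. Table 1 schedules body weight at Dose 1 and at Dose 2, and urine is pooled from arrival to departure. The stated change comparison uses none of these records.

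**The concern.** The two sides of the comparison are different quantities. The change in PV+ISV between two times is fluid lost minus fluid gained and retained in that space. The volume removed by dialysis is only the main loss. These patients are oliguric, so urine offsets little of what they drink.

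A Bland-Altman plot shows any mean difference as bias. If patients drink between the doses, a perfect method would show an offset against volume removed, and differing intake would widen the limits of agreement. Iohexol would shift in the same direction, so its own comparison with volume removed could not separate intake from method error. The risk is that an offset caused by the reference is carried forward as a property of the method.

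There is also a point of wording. The text does not say whether the PV change, the ISV change or their sum is set against volume removed. Only the sum can be expected to agree with it.

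**Working it through.** **Interval.** Table 2 gives 180 min of sampling + 4 h dialysis + 1 h equilibration = 8 h, which reproduces the stated figure. The narrative (Dose 1 about 4 h before dialysis, Dose 2 about 1 h after) gives 4 + 4 + 1 = 9 h. These passages should be reconciled; I use 8 h.

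**Formula.** Let U be the volume removed, W the fluid gained between the doses, and f the share of W that stays in PV+ISV. An error-free method shows a fall of U − f × W, so the shortfall against U is f × W.

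Assumptions:
- f is not in the documents; I take 1/3 to 1.
- U is drawn wholly from PV+ISV.
- Each measurement refers to its dose time.
- Smaller terms are left out. Urine, blood draws and insensible loss work the other way; rinseback fluid adds to the shortfall. Blood drawn after Dose 1 up to the Dose 2 predose sample is 7 + 7 + 4 + 7 + 7 + 4 + 7 = 43 mL by Table 2.

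**Illustration from the protocol's figures.** The gain comes from 7.1, item 7: "Patients must have an average interdialytic weight gain of at least 2 kg". For the time over which it accrues, 4.6.2 says "The second dose of VFI and Iohexol will be removed between 36 and 48 hours later at the first follow-up dialysis session", while the Synopsis puts the next sessions about 2 to 3 days after Day 1 (48 to 72 h). Together T = 36 to 72 h. With even accrual, W = 2 × 8/T:

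| T | W (L) | Shortfall, f = 1/3 to 1 (L) | Share of U, if U = 2 L |
|---|---|---|---|
| 36 h | 0.44 | 0.15 to 0.44 | 7.4 to 22.2% |
| 48 h | 0.33 | 0.11 to 0.33 | 5.6 to 16.7% |
| 72 h | 0.22 | 0.07 to 0.22 | 3.7 to 11.1% |

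If U equals the gain, the share is f × 8/T and does not depend on the size of the gain. Interdialytic gain is net of losses and includes food, so this W is a net figure.

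**Heavier drinking.** Here W is gross water.
- The 1.5 L cap drunk evenly over 8 + 3 = 11 h: 1.5 × 8/11 = 1.09 L in the interval, shortfall 0.36 to 1.09 L.
- The whole cap between the doses: shortfall 0.5 to 1.5 L, an outer bound.

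**What a correction leaves.** Subtracting a share g of W leaves an error of (f − g) × W.
- W = 0.44 L: g = 0 leaves +0.15 to +0.44 L; g = 2/3 leaves −0.15 to +0.15 L; g = 1 leaves −0.30 to 0 L.
- W = 1.5 L: g = 2/3 leaves −0.5 to +0.5 L; g = 1 leaves −1.0 to 0 L.

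Full subtraction over-corrects for every f below 1, and is worse than no correction when f is below 1/2.

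**The case against.** The protocol does not claim that the change equals the volume removed. Its list of analyses is open, it excludes no adjustment, and it already requires the water record, both weights and pooled urine. How these enter the analysis could be left to a statistical analysis plan, and the study is an unpowered pilot of about 10 (11.1). That limits how serious the point is. It does not remove it: the reference is fixed in the primary endpoint, and the plan followed as written compares two different quantities.

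A reader might infer that the offset will be taken for a fault of FAST. The documents do not support that. FAST is also compared with iohexol at each dose. If the two agree there and both fall short of volume removed, that argues against a FAST-specific bias, though it would not identify intake as the cause.

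A reader might also take 1.5 L as the expected error. Section 8.2 gives a ceiling for water and no times, so how much falls between the doses is unknown.

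Finally, every size here rests on assumed f and W, and the result moves with the protocol's own timing: 36 to 48 h alone would give 6 to 22%, 48 to 72 h would give 4 to 17%. This stands, and is why the full range is shown.

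**Conclusion.** The point holds in a limited form. The stated reference omits fluid gained between the measurements, so an accurate method would be expected to show a smaller fall than volume removed. On the illustration the shortfall is about 0.07 to 0.44 L, roughly 4 to 22% of the volume removed. This assumes even accrual over 36 to 72 h, a retained share of 1/3 to 1, and removal equal to the gain and wholly from PV+ISV. Section 4.1 calls dry-weight changes of 0.6 to 1 kg clinically significant; the illustration stays below that range, and heavier drinking could reach it.

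It would go too far to infer that the study's conclusion is invalidated. The protocol sets no agreement margin, so no pass or fail decision changes, and the FAST versus iohexol comparison at each dose is unaffected. The risk is a misread bias in a pilot, and it is cheap to guard against.

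**What to change.** 1. Keep the comparison with volume removed. State that the change in PV+ISV is the quantity for Bland-Altman agreement, and report the separate PV and ISV changes descriptively.
2. Pre-specify a second comparison with net fluid balance over the interval. Use the Dose 1 to Dose 2 body-weight change already scheduled as the simplest reference. As a sensitivity analysis, use volume removed minus recorded intake, with the share varied from 1/3 to 1.
3. Make sure the CRF water entry shows whether intake fell before or after Dose 2. The CRF is not shown, so it may already do so.

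The cost is wording in the endpoint and analysis sections, possibly one CRF field, and a little more analysis. The downside is that neither new reference is exact. Body weight carries weighing error and food weight, and it counts all intake wherever it goes, so it acts like g = 1 and can over-correct. The intake version depends on an assumed share: moving g from 1/3 to 1 shifts the reference by (2/3) × W, or 0.15 to 0.30 L for W of 0.22 to 0.44 L and 1.0 L for W of 1.5 L. It also leaves out urine, blood draws, rinseback and insensible loss unless they are added. Both the unadjusted and the net-balance results should therefore be reported. No change to the fluid allowance is proposed.

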9.5.2.2. Other Tests

A certified laboratory will be utilized to process and provide results for the additional lab tests listed below, to be drawn prospectively for the study unlike the baseline tests listed in [Table 6](#).

- Pregnancy test (nonmenopausal females only)
- nT Pro-BNP

- Creatinine phosphokinase
- Liver function tests: Alanine aminotransferase (ALT), aspartate aminotransferase (AST), and total bilirubin
- Timed Urine Collection (patient arrival to departure on visit 2) for:
 - Total Volume
 - Creatinine
 - Urea Nitrogen

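### Table 2 schedules 81 mL of blood on Day 1 against the protocol's own limit of 80 mL per 24 hours, and the Day 1 safety blood comes on top

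*Protocol*

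**What the plan says.** Table 2 (Section 1, Synopsis) lists 13 performance draws on Day 1 with a volume for each. The first row reads "Predose (within 30 minutes) X X 6 mL". A typical row with both samples reads "15 minutes X X 7 mL". Rows with a FAST sample only are 4 mL. Footnote b gives the make-up: "Each blood draw will be taken as follows: 1 mL waste draw, 3mL FAST blood sample, 3 mL Iohexol Sample". The note beneath the table sets the limit, whatever the timing or number of draws: "no subject will have more than 80 mLs blood drawn for this study within a 24-hour period".

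Other blood is taken on the same day. Table 1, footnote h: "BUN and serum creatinine will be drawn pre-dose dose 1 and post the dose 2 180 min VFI blood draw". Section 9.5.2.2 lists further tests that are "to be drawn prospectively for the study unlike the baseline tests listed in" Table 6. Among them are NT-proBNP, CPK and "Liver function tests: Alanine aminotransferase (ALT), aspartate aminotransferase (AST), and total bilirubin", and Table 1 marks all three for Day 1. Neither table nor Section 9.5.2.2 gives a volume for any of these.

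The only priority rule is the note to Table 1: "the timing of performance blood sample collections will take priority over all other scheduled activities". It applies when several postdose procedures fall at the same nominal time.

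**The concern.** A schedule and a safety limit printed in the same table should agree, and these do not. The limit covers all blood drawn for the study. The performance draws alone pass it, and the safety blood is neither counted in Table 2 nor exempted from the limit.

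A site that takes every listed draw breaks the limit. A site that respects the limit must leave something out, and the Protocol does not say what. Either course is a deviation as Section 13.1.1 defines it, and Section 13.1 warns that a deviation can make a subject non-evaluable. The pressure comes at the end of the day, at the last Dose 2 performance samples and the closing BUN and creatinine. The Dose 2 samples feed the post-dialysis PV and ISV measurements and their comparison with the volume removed, both primary endpoints in Section 11.3.1. The conflict arises for each of the up to 10 patients who completes Day 1 as scheduled.

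**Working it through.** **Inputs.** Volumes, make-up of each draw and the 80 mL limit are from Table 2, its note and footnote b. The timing of safety blood is from Table 1 and Section 9.5.2.2.

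**All draws fall in one 24-hour period.** Table 2 puts Dose 2 about 8 h after Dose 1, so the last draw is at about 8 + 3 = 11 h. Counting about 4 h from Dose 1 to dialysis, 4 h of dialysis and 1 h of equilibration gives 4 + 4 + 1 + 3 = 12 h. The first predose draw adds at most 30 minutes.

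**Running total of the printed volumes.**

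| Draw | mL | Cumulative mL |
|---|---|---|
| Dose 1 predose | 6 | 6 |
| 15 min | 7 | 13 |
| 60 min | 7 | 20 |
| 80 min (FAST only) | 4 | 24 |
| 120 min | 7 | 31 |
| 180 min | 7 | 38 |
| Pre-rinseback (FAST only) | 4 | 42 |
| Dose 2 predose | 7 | 49 |
| 15 min | 7 | 56 |
| 60 min | 7 | 63 |
| 80 min (FAST only) | 4 | 67 |
| 120 min | 7 | 74 |
| 180 min | 7 | 81 |

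By period: 38 + 4 + 39 = 81 mL. Excess over the limit: 81 − 80 = 1 mL.

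**Split into samples and waste.** Ten draws carry both samples: 10 × 6 = 60 mL. Three carry FAST only: 3 × 3 = 9 mL. Analytical blood is 60 + 9 = 69 mL. Waste is 81 − 69 = 12 mL, that is 1 mL in each of 12 draws. The first predose draw, at 6 mL, has room for its two samples only.

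**Other readings of the table.**

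- Footnote b applied to the first predose draw (7 mL): 82 mL.
- Pre-rinseback draw left out: 81 − 4 = 77 mL.
- All waste left out: 69 mL.

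Only the last two fall below 80 mL. Neither fits the text: the pre-rinseback draw is a listed study sample, and the column records blood drawn, with the 1 mL waste included in its values.

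**Safety blood.** Footnote b uses up each listed volume, so safety tubes are extra. Let S1 be the safety blood taken before Dose 1 and S2 the closing BUN and creatinine. The Day 1 total is 81 + S1 + S2, with S1 and S2 not stated.

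- Room left before the Dose 2 180-minute draw, with waste as listed: 80 − (74 + S1) = 6 − S1 mL. Its two samples need 6 mL, so they just fit if S1 = 0 and fall short for any S1 above 0.
- The closing BUN and creatinine come after 81 mL on the listed volumes, so S2 lies wholly above the limit.
- If no waste is counted, the room for all safety blood is 80 − 69 = 11 mL.

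Table 1 also marks a predose hematocrit at both doses, again without a volume. If it needs its own blood, that adds to the total.

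**The case against.** The strongest reply is that the demonstrated excess is 1 mL. Leaving out one waste draw brings Table 2 to exactly 80 mL with no sample lost, and all 69 mL of analytical blood fits with 11 mL to spare. That is correct, and no clinical harm is claimed.

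A second reply is that the limit is worded to override the schedule, so a compliant site stops at 80 mL and the patient is protected. That reading protects the patient but leaves the conflict: the schedule then cannot be completed as listed, and the Table 1 note ranks timing, not volume. That note does favour performance sampling, so a site would more naturally give up waste than endpoint samples.

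Third, tube volumes are operational detail often kept outside a protocol, so the excess beyond 1 mL is not a computed error. This stands as a limit on size. It does not change the fact that the limit covers study blood that the Table 2 volumes leave out. The effects on the 180-minute samples and the closing BUN and creatinine are conditional on the waste being drawn as listed, and the first also on some predose safety blood being counted.

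Finally, the 6 mL first entry is readable as two samples without waste. It needs clarifying and would not be a finding by itself.

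**Conclusion.** The concern holds. The draws listed in Table 2 total 81 mL within about 12 hours against a stated limit of 80 mL per 24 hours. The 1 mL excess is exact from the printed volumes and needs no assumption beyond taking them as written. The full excess is 1 mL plus the Day 1 safety blood, and cannot be sized from the Protocol.

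This is an internal contradiction with a stated safety limit. It is not a clinical danger, and loss of endpoint samples is possible but not shown. It merits correction because the Protocol's own schedule cannot meet the limit as written and the remedy costs almost nothing.

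**What to change.** 1. Add up all Day 1 study blood, including the tubes for BUN and creatinine, CPK, liver tests, NT-proBNP and, where they need separate blood, hematocrit and the pregnancy test. State the total under Table 2 and say that the limit covers it.
2. Then either raise the limit to that total, aligning the consent text if it gives a limit, or keep 80 mL and cut volume. Reducing or returning the 1 mL waste draws takes Table 2 down to as little as 69 mL and leaves up to 11 mL for safety tubes. If the tubes need more than 11 mL, the limit has to rise or the sample volumes have to shrink.
3. In the same edit, say whether the 6 mL first predose draw is meant to have no waste, and state that the Dose 2 FD001, FD003 and iohexol samples are kept if the limit is approached.

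The cost is wording in Table 2 and its notes, and in the consent text if the limit is raised. No patients, visits or samples are added.
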